###### *Secondary:*

Pregnancies ending in spontaneous abortion, defined as spontaneous losses before 20 weeks of gestation, and identified using ICD-10-CM diagnosis and procedure codes.

Pregnancies ending in stillbirth, defined as *in utero* fetal deaths 20 weeks of gestation and after, and identified using ICD-10-CM diagnosis and procedure codes.

Small-for-gestational age in live-born infants, defined as birth weight 10th percentile, and identified using ICD-10-CM diagnosis codes.

##### *Exposure Variable*

Exposure to erenumab-aooe will be defined as having a pharmacy claim for erenumab-aooe (identified through NDC codes) in the 112 days prior to the estimated last menstrual period or during the pregnancy.

##### *Other Covariates*

Other covariates will include maternal demographics, reproductive history, comorbidities, concomitant medication use, and other risk factors for adverse maternal, fetal, and infant outcomes.

Validation of select study variables will be performed in the HIRD. Medical record/electronic health records will be sought to validate claims-identified outcomes for major congenital malformations, spontaneous abortion, still birth, and LMP. Similar to other pharmacoepidemiologic database validation studies, this validation study will provide estimates of positive predictive value (PPV) for each of the endpoints. In addition, a validation study of the algorithm to identify migraine cases and estimate the PPV of the algorithm will also be undertaken.

#### Study Sample Size

In the MarketScan CCE database, feasibility estimates for years 2010-2014 indicate there are annually approximately 7,000 women with migraine who have a pregnancy indicator. In contrast, the HIRD included 11,704 pregnant women with migraine for calendar year 2017. Analyses will be conducted separately for each database and pooled if appropriate. The sample size calculations described below were based on estimates from the MarketScan CCE database, the smaller of the two databases.

We estimate that approximately 0.9% of pregnant women with migraines will be treated with a migraine preventive medication during pregnancy. Based on the projected uptake of erenumab-aooe in migraine patients, we estimate that approximately 1,400-1,500 women with migraine will be exposed to erenumab-aooe during pregnancy in the MarketScan® database for the time period 2018-2027. The actual number will vary depending upon the utilization of erenumab-aooe treatment by the source population in the MarketScan® CCE database. Assuming that we will have an equal number of women with migraine in the comparator cohorts and a background prevalence of the outcome of  $\geq 3\%$ , we will have at least 80% power to detect an odds ratio of 2.00 or higher.

Approximately 75-80% of pregnancies end in live births and taking into account the 77% mother-infant linkage rate in the MarketScan® CCE database, it is estimated that we will have approximately 120 infants for which outcomes may be assessed. As above for pregnancy outcomes, there is limited power to detect moderate differences in outcomes that are relatively rare.

- Data Analysis

Descriptive interim analyses will be conducted annually, CCI

The final report will be provided in November 2028. Within each database, for each cohort, these reports will provide overall counts of patients (pregnant mothers and infants), descriptive statistics for baseline patient characteristics, and the proportion (95% confidence intervals [CI]) for outcomes of interest. In addition, occurrence of incident medical conditions (eg, gestational diabetes) and use of new medications during the follow-up period will be summarized.

Discrete variables will be summarized using frequencies and proportions, and continuous variables will be summarized using means and standard deviations (SD) or medians and interquartile range (IQR), as appropriate.

- Comparative Analyses

Assuming sufficient power to detect a risk of ratio  $\geq 2.0$  and adequate overlap in the distribution of confounding variables, comparative analyses will be initiated. Balance in covariate distributions will be evaluated by standardized mean differences (SMDs), with an SMD  $< 0.10$  indicating good balance. The potential comparative analyses are summarized below:

- (1) Effect of erenumab-aooe versus other preventive migraine medications on spontaneous abortions (and, separately, stillbirths), in pregnant women with migraine.
- (2) Effect of erenumab-aooe versus other preventive migraine medications on congenital malformations (and, separately, 'small-for-gestational-age'), in live-born infants of women with migraine.

These analyses will be replicated using alternate comparator groups that were unexposed to erenumab-aooe. For the comparative analyses, the effect measure of interest will be the odds ratio (95% CI). We will account for confounding with inverse probability of treatment weights (IPTWs).

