### **9.5 Study Size**

Feasibility estimates for the years 2010-2014 indicate that annually we will be able to identify approximately 7,000 pregnant women with migraine from the MarketScan CCE database. In contrast, as of 2017, the HIRD included 11,704 pregnant women with migraine. Analyses will be conducted separately for each database and pooled if appropriate. The sample size calculations described below were based on estimates from the MarketScan CCE database, the smaller of the two databases.

We estimate that approximately 0.9® of pregnant women with migraine will be treated with a migraine preventive medication during pregnancy. Based on the projected uptake of erenumab-aooe in migraine patients, we estimate that from May 2018 through May 2027 approximately 1,400-1,500 pregnant women in the MarketScan CCE database with migraine will be exposed to erenumab-aooe during their pregnancy. The actual number will vary depending upon the utilization of erenumab-aooe treatment by the source population in the MarketScan CCE database.

Sample sizes for the comparison of the primary outcome (major congenital malformations) are calculated assuming a 3® prevalence of major congenital malformations in infants of women with migraine, a 62® live birth rates of pregnancies, 1:4 matching of the erenumab-aooe exposed to the comparator cohorts, and 80® power. In past studies in HIRD involving linkage of mothers and their infants, approximately 72-85® of completed pregnancies could be connected to a qualifying infant ([Mines et al, 2014](#); [Nkhoma et al, 2012](#)). In the MarketScan databases, the

mother-infant linkage is approximately 77%. The study will have at least 80% power to detect at least a 2-fold increase in the risk of major congenital malformations (Table 2).

**Table 2. Required Sample Size Estimates and Relative Risks for the Comparison of Major Congenital Malformations Between the Erenumab-aooe Exposed Cohort and the Unexposed Cohorts**

Relative Risk	Sample size of pregnant women in the exposed group, accounting for 62% live birth rate	Sample size of live births, accounting for a 77% mother-infant linkage rate	Sample size of live births in the exposed group
1.25	11,731	7,273	5,600
1.50	3,142	1,948	1,500
1.75	1,181	909	700
2.00	717	522	425
2.25	597	370	285
2.75	270	208	160
3.00	210	162	125

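### The study-size inputs in the Abstract and Section 9.5 conflict, and the stated 0.9% preventive use does not support 1:4 matching or 80% malformation power against comparator A in MarketScan

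*Protocol*

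**What the plan says.** The Abstract (Study Sample Size) bases the calculation on MarketScan, the smaller database, where "feasibility estimates for years 2010-2014 indicate there are annually approximately 7,000 women with migraine who have a pregnancy indicator". It then says "approximately 0.9% of pregnant women with migraines will be treated with a migraine preventive medication during pregnancy" and, citing projected uptake without giving an uptake figure, "approximately 1,400-1,500 women with migraine will be exposed to erenumab-aooe during pregnancy in the MarketScan® database for the time period 2018-2027". It continues "Assuming that we will have an equal number of women with migraine in the comparator cohorts", and claims at least 80% power for an odds ratio of 2.00 at a background of 3% or more. For infants it applies 75-80% live births and 77% linkage: "it is estimated that we will have approximately 120 infants for which outcomes may be assessed". It adds that power for rare outcomes is limited.

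Section 9.5 repeats the 7,000 and the 0.9%. For May 2018 to May 2027 it gives this projection: "approximately 1,400-1,500 pregnant women in the MarketScan CCE database with migraine will be exposed to erenumab-aooe during their pregnancy". For malformations it assumes 3% prevalence, 62% live births, 77% linkage and "1:4 matching of the erenumab-aooe exposed to the comparator cohorts", and concludes: "The study will have at least 80% power to detect at least a 2-fold increase in the risk of major congenital malformations". Section 9.2.3 also plans 1:4 matching.

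Comparator A is women using other preventives and comparator B is women using none. No expected count is given for either.

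**The concern.** Erenumab is a migraine preventive, so its users should be a subset of preventive users. As written, the subset is about two and a half times the whole. If 0.9% was meant to exclude erenumab, it is the only figure in the protocol that bears on the size of comparator A, and it is too small for a 1:4 match. Separately, the 120 infants cannot be obtained from the numbers around it, so a reader of the Abstract and a reader of Section 9.5 reach opposite views of feasibility.

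This matters because the comparative analyses start only if power is judged sufficient for a risk ratio of 2.0, and Section 9.6.1.1 ties the annual assessment to 425 exposed, a count derived at 1:4. That count could be reached while the comparison with other preventives, the one listed first in the Abstract's Comparative Analyses, remains underpowered. A null result there could then be read as reassurance.

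**Working it through.** **Inputs.** 7,000 pregnancies a year, 0.9%, 1,400-1,500 exposed, 77% linkage and 3% background (Abstract and Section 9.5); nine years, 62% live births and 1:4 (Section 9.5); 75-80% live births and 1:1 (Abstract). Two-sided 5% is assumed from the planned 95% intervals. Power is for two proportions, with pooled variance under the null and no continuity correction.

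**Check of the formula.** For RR 2.0 (6% vs 3%), 1:4 and 80% power, Table 2 gives 425 exposed live births. The formula gives 428, and 425 vs 1,700 has 79.8% power. The method therefore reproduces the plan's own figure.

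**1. Infants.**
- Abstract inputs: 1,400 x 0.75 x 0.77 = 808; 1,500 x 0.80 x 0.77 = 924.
- Section 9.5 rate: 1,400 x 0.62 x 0.77 = 668; 1,500 x 0.62 x 0.77 = 716.
- Working back, 120 infants imply 120 / (0.80 x 0.77) = 195 to 120 / (0.75 x 0.77) = 208 exposed pregnancies.
- With 120 exposed infants, power for RR 2.0 is 20% at 1:1 and 38% at 1:4.

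**2. The 0.9% against the projection.**
- 7,000 x 9 = 63,000; 63,000 x 0.009 = 567 (630 over ten years).
- 1,400 / 63,000 = 2.2%; 1,500 / 63,000 = 2.4%.

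**3. The 1:4 match to comparator A, if 0.9% means other preventives only.**
- Needed for all exposed: 4 x 1,400 = 5,600 to 4 x 1,500 = 6,000.
- Needed at Table 2's minimum: 425 / (0.62 x 0.77) = 890 exposed pregnancies, and 4 x 890 = 3,560. Table 2 prints 717 for this row, which does not follow from its own rates (717 x 0.62 x 0.77 = 342).
- Available: 567 in MarketScan, or (7,000 + 11,704) x 9 x 0.009 = 1,515 in both databases, taking HIRD's 2017 count as annual.

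**4. Power for malformations, RR 2.0.**

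| Comparison | Linked infants | Power |
|---|---|---|
| A, MarketScan, 62% live births | 668-716 vs 271 | 47% |
| A, MarketScan, 75-80% live births | 808-924 vs 327-349 | 55-59% |
| A, MarketScan, 80%, 1,500 exposed, ten years (630 in A) | 924 vs 388 | 63% |
| A, pooled comparators, 1,400 exposed | 668 vs 723 | 77% |
| A, pooled, exposure scaled to both databases | 1,786 vs 723 | 90% |
| B, MarketScan, 1:4 | 668 vs 2,672 | 93% |

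Here 271 = 567 x 0.62 x 0.77; 723 = 1,515 x 0.62 x 0.77; and 1,786 = 1,400 x (18,704 / 7,000) x 0.62 x 0.77. With 668 vs 271, 80% power is reached at an RR of about 2.55.

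**5. The Abstract's pregnancy-level claim (OR 2.00, 3%).** At 1,400-1,500 per group, power is 95-96%. Against 567 comparators it is 77-78% for an OR of 2.0 and 81-82% for an RR of 2.0.

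**The case against.** The strongest reply is that 1,400-1,500 is attributed to projected uptake, not to the 0.9%, so 567 does not displace it. That stands. A reader might infer that the true exposed count is 567, but the documents do not support this: they give neither the population and period behind 0.9% nor the uptake assumption. The closeness of 1,515 to 1,500 does not show that the projection is a two-database total either, since both sections assign it to MarketScan and to erenumab.

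Second, 567 is not a ceiling for comparator A. Section 9.2.2.1 also admits use within five half-lives before LMP, while 0.9% covers use during pregnancy. That also stands, but the pool would have to grow about sixfold (3,560 / 567) for the Table 2 minimum and about tenfold (5,600 / 567) for all exposed. The exclusion of known teratogens and other CGRP antagonists works the other way.

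Third, a reader might infer that 80% power is unattainable throughout. It is not: comparator B is easily matched at 1:4, the pregnancy-level claim stays close to or above 80%, and pooling is allowed. Nor does the Abstract's 1:1 ratio fail by itself. With its own 808-924 infants per group, power for RR 2.0 is 83-88%.

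Finally, comparisons are conditional on sufficient sample size and exposed counts are re-projected every year from year three. That limits the harm, but it does not correct the figures or supply a comparator A count.

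**Conclusion.** The point holds in a limited form. Whatever 0.9% means, the 120 infants is wrong on the Abstract's own inputs by a factor of about seven to eight (808-924 against 120), and the Abstract and Section 9.5 disagree on ratio, live-birth rate and power conclusion. As worded, 0.9% (about 567) cannot contain 1,400-1,500 erenumab users.

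If 0.9% means other preventives only, 1:4 matching to comparator A is out of reach, and MarketScan power for RR 2.0 in malformations is about 47%, or 55-63% under the more generous live-birth and accrual assumptions, not at least 80%. This rests on about 567 comparator A pregnancies, 3% background, two-sided 5% and unweighted proportions. The detectable RR of about 2.55 depends on the same count and is not a settled replacement value. Comparator B and the pregnancy-level claim are not materially affected.

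**What to change.** - Use one exposed count (with its database named), one live-birth rate and one ratio in the Abstract and Section 9.5.
- Replace the 120 infants with the figure those inputs give, and align the two statements about power.
- State the population and period behind 0.9%, whether it includes erenumab, and the uptake assumption behind 1,400-1,500.
- Give an expected comparator A count that allows for the pre-LMP window and the exclusions.
- State power and detectable RR separately for A (at the attainable ratio, for MarketScan alone and pooled) and for B (at 1:4). Limit the 80% claim to the comparisons that reach it.
- Show an RR of about 2.55 against A only as conditional on 567 comparator A pregnancies.

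The cost is a rewrite of the study-size text and the work of obtaining a comparator A count. No design or data change is needed, though the stated power against A is likely to become less favourable.

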## 5. Amendments and Updates

None

## 6. Milestones

Milestone	Planned date
CCI	
Start of data collection	Nov 2020
End of data collection	Nov 2027
Annual interim reports	Nov 2021 – Nov 2027
Registration in the EU PAS register	Oct 2020
Study completion	Nov 2027
Final report of study results	Nov 2028

## 7. Rationale and Background

### 7.1 Diseases and Therapeutic Area

Migraine is a neurological disorder characterized by recurrent headache attacks of moderate to severe pain. Migraines affect up to 18% of the female population and 6% of the male population; the prevalence peaks in middle life (30 to 49 years) (7.9%-9.0% in men and 25.5%-28.1% in women) and is lower in children/adolescents and those older than age 60 (Lipton et al, 2007).

Treatment for migraine includes medications for acute migraine as well as preventive medications. Acute treatments that are commonly used for migraine attacks include triptans, ergots, nonsteroidal anti-inflammatory drugs (NSAIDs), acetaminophen, and antiemetic agents (Charles 2017). The most commonly used therapies for migraine prevention include tricyclic antidepressants, beta-blockers, anticonvulsants (eg, topiramate and divalproex sodium), and botulinum toxin (Charles 2017).

Migraine often improves during pregnancy; however, this varies depending on whether women have migraine with aura. For patients who have migraine without aura, approximately 47% of women will have improvement or remission of migraine in the first trimester, increasing to 83% in the second trimester, and 87% in the third trimester (Sances et al, 2003). Migraine with aura is less likely to improve during pregnancy (Robbins 2018).

Up to 70% of pregnant women with migraine require a behavioral or a pharmacologic intervention (Contag et al, 2009). Although nonpharmacologic therapies are recommended for migraine management during pregnancy, acute medications used to treat migraine include acetaminophen and metoclopramide; however, narcotics, NSAIDs (depending on the trimester) and triptans may also be used (Robbins 2018). Triptans

are classified as an FDA category C drug. Data from a prospective pregnancy registry observed birth defects in 4.2% (95% confidence interval (CI) 2.6%-6.5%) of infants born to women using sumatriptan during pregnancy (Ephross and Sinclair 2014), which is consistent with general population birth defect rates. Preventive medications that may be used during pregnancy include memantine and beta blockers, such as propranolol (Robbins 2018). Beta-blockers are generally thought to be safe and are commonly used to treat hypertension in pregnant women; however, they may be associated with intrauterine growth restriction (Robbins 2018). Topiramate and valproic acid should be avoided during pregnancy due to their teratogenic effects (Robbins 2018; Hernandez-Diaz et al, 2012).

Erenumab-aooe is a human monoclonal antibody (mAb) that inhibits the receptor for calcitonin gene related peptide (CGRP) and is indicated for the preventive treatment of migraine. Although clinical trials have demonstrated erenumab has a favorable risk benefit profile, there are no adequate and well-controlled studies on the use of erenumab-aooe in pregnant women. In animal reproduction studies, there were no effects on pregnancy or neonatal/infant development when monkeys were administered erenumab-aooe SC from organogenesis through parturition at exposures up to 16-fold the exposure at the maximum recommended human dose of 140 mg monthly.

## 7.2 Rationale

This study is being conducted to address post-marketing requirements CCI [REDACTED] to assess the safety of erenumab-aooe on maternal, fetal, and infant outcomes resulting from the use of erenumab-aooe during pregnancy. This proposed study leverages two large US administrative claims databases to allow for longitudinal follow-up of patient outcomes. Additionally, the study will provide an accurate reflection of how patients are treated in community practice settings and assess erenumab-aooe utilization patterns versus other preventive and acute medications being used by pregnant women suffering from migraines.

## 7.3 Statistical Inference (Estimation or Hypothesis)

If there is sufficient sample size and adequate overlap in the distribution of confounding variables, we will evaluate the null hypothesis of no effect of treatment on the four outcomes of interest. The proportion of spontaneous abortions, and, separately, stillbirths will be estimated and compared in pregnant women with migraine. Also, the proportion of major congenital malformations and, separately, 'small-for-gestational-age' will be estimated and compared in live-born infants of women with migraine.

## **8. Research Question and Objectives**

### **8.1 Primary**

The primary objective is to estimate and compare the proportion of live-born infants with major congenital malformations among (1) women with migraine directly exposed to erenumab-aooe prior to and during pregnancy, (2) women with migraine exposed to other preventive migraine medications prior to or during pregnancy (comparator group A), and (3) women with migraine not exposed to erenumab-aooe or other preventive migraine medications prior to or during pregnancy (comparator group B). Comparative analyses will be undertaken if there is sufficient sample size and adequate distribution of covariates to adjust for confounding.

### **8.2 Secondary**

1) To estimate and compare the proportion of pregnancies ending in spontaneous abortions, and, separately, stillbirths among (1) women with migraine directly exposed to erenumab-aooe prior to and during pregnancy, (2) women with migraine exposed to other preventive migraine medications prior to or during pregnancy (comparator group A), and (3) women with migraine not exposed to erenumab-aooe or other preventive migraine medications prior to or during pregnancy (comparator group B).

Comparative analyses will be undertaken if there is sufficient sample size and adequate distribution of covariates to adjust for confounding.

2) To estimate and compare the proportion of live-born infants who are small-for-gestational age among (1) women with migraine directly exposed to erenumab-aooe prior to and during pregnancy, (2) women with migraine exposed to other preventive migraine medications prior to or during pregnancy (comparator group A), and (3) women with migraine not exposed to erenumab-aooe or other preventive migraine medications prior to or during pregnancy (comparator group B). Comparative analyses will be undertaken if there is sufficient sample size and adequate distribution of covariates to adjust for confounding.

3) To describe demographic and clinical characteristics, risk factors for adverse pregnancy outcomes, fetal outcomes, and infant outcomes, and medication treatment patterns during pregnancy in both exposed and unexposed cohorts of women with migraine.

## **9. Research Methods**

### **9.1 Study Design**

Retrospective observational cohort study

### **9.2 Setting and Study Population**

This study will use data from the following two large commercial claims databases: (1) The Commercial Claims and Encounters (CCE) database from the IBM Watson Health (formerly Truven Health) MarketScan® Research Databases is a large convenience sample of individuals with employer-sponsored private insurance which includes claims from more than 200 US commercial health plans, and (2) the HealthCore Integrated Research Database (HIRD) is a nationwide proprietary, fully integrated, longitudinal commercial claims database with 72.5 million unique individuals. Both claims databases contain information on prescription fills and medical encounters

These databases contain de-identified information on geographically diverse, commercially insured patients in the US. Diagnoses, procedures, and drug dispensings are captured with the following standard coding systems: International Classification of Diseases, 10th Revision, Clinical Modification (ICD-10-CM), Common Procedural Terminology (CPT), National Drug Codes (NDC), Healthcare Common Procedure Coding System (HCPCS), and Diagnostic Related Groups (DRGs).

